### **8.5.10 Medication error**

Medication error refers to any unintentional error in the dispensing or administration of an IMP.

Medication errors include accidental overdose or underdose, inappropriate schedule of product administration, incorrect route of product administration, wrong product administered, and expired product administered.

Accidental overdose or underdose where a clinical consequence occurred or could have occurred should be recorded based on investigator judgement.

Inappropriate schedule of product administration where a clinical consequence occurred or could have occurred should be recorded based on investigator judgement.

Treatment non-compliance (including missed doses) where no clinical consequence occurred or could have occurred should not be recorded as medication errors. See Section [6.3.2](#) for recording of treatment compliance.

Medication error must be recorded on the AE form in the eCRF. In addition, any clinical consequences of the medication error must be recorded as separate AEs on the AE form. If the AE originating from the medication error qualifies as an SAE, expedited reporting is required (Section [8.5.7](#)).

### **8.5.11 Misuse or Abuse**

The terms misuse and abuse are similar in that they both represent the intentional use of a drug in a way other than defined in the protocol.

Misuse refers to situations where the IMP is intentionally and inappropriately used for therapeutic purposes not in accordance with the protocol.

Abuse refers to intentional use of an IMP for what could be considered desirable non-therapeutic effects (e.g. sedative, stimulant, euphoric effects).

Misuse and abuse must be recorded on the AE form in the eCRF. In addition, any clinical consequences of misuse or abuse must be recorded as separate AEs on the AE form. If the AE originating from the misuse or abuse qualifies as an SAE, expedited reporting is required (Section [8.5.7](#)).

### **8.5.12 Aggravation of condition**

Any clinically significant aggravation/exacerbation/worsening of any medical condition(s) compared to screening must be reported as an (S)AE in accordance with Section [8.5.5](#).

Worsening of FFA is captured by efficacy assessments and will not be recorded as an AE.

## **8.6 Procedural Complications (Cohort 2 Only)**

For subjects in Cohort 2, procedural complications will be reported instead of AEs.

For the purpose of this trial, a procedural complication is defined as any untoward medical event experienced by a subject that has signed an ICF for the trial, such as infection, bleeding, and/or pain, that the investigator believes to be causally related to the trial procedures performed at Day 1 visit or at the optional visit. Subjects will receive appropriate treatment as needed for any procedural complications that arise.

For the purpose of this trial, a serious procedural complication is any untoward medical event related to the trial procedures that has any of the following consequences:

- Results in death
- Is life-threatening
- Requires in-patient hospitalization or prolongation of existing hospitalization
- Results in persistent or significant disability/incapacity

Note: The term “life-threatening” in the definition of “serious” refers to an event in which the subject was at risk of death at the time of the event; it does not refer to an event that hypothetically might have caused death if it were more severe.

Any medical condition that is present prior to the first sample collection on Day 1 will be considered as part of medical history and not reported as a procedural complication. Should a subject experience an event that he believes to be causally related to the trial procedure performed on Day 1 or at the optional follow-up visit (after sample collection), the event will be recorded as a procedural complication. Any procedural complications whether observed by site personnel or reported spontaneously by the subject will be described in the source document and eCRF.

Any serious procedural complication (this refers to any procedural complication that meets one or more of the aforementioned serious criteria) occurring during the trial must be reported on a serious procedural complication form as per the instructions in Section [8.5.7](#).

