### **8.5 Adverse Events and Serious Adverse Events (Cohort 1 Only)**

#### **8.5.1 Definition of Adverse Event**

An AE is any untoward medical occurrence in a subject administered a pharmaceutical product and that does not necessarily have a causal relationship with this treatment. An AE can therefore be any unfavorable and unintended sign (including an abnormal laboratory finding), symptom, or disease temporally associated with the use of an IMP, whether or not considered related to the IMP.

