#### **8.5.3 Definition of Serious Adverse Event**

A SAE is any untoward medical occurrence that, at any dose has any of the following consequences:

- Results in death
- Is life-threatening
- Requires in-patient hospitalization or prolongation of existing hospitalization
- Results in persistent or significant disability/incapacity
- Is a congenital anomaly/birth defect
- Is a medically important condition. Events that may not be immediately life-threatening or result in death or hospitalization but may jeopardize the subject or may require intervention to prevent one of the other outcomes listed in the definition above. Examples are intensive treatment in an emergency room or at home for allergic bronchospasm, blood dyscrasias, and convulsions that do not result in hospitalization, development of drug dependency, or drug abuse.

Note: The term “life-threatening” in the definition of “serious” refers to an event in which the subject was at risk of death at the time of the event; it does not refer to an event that hypothetically might have caused death if it were more severe.

Note: Hospitalization for procedures or treatments planned prior to the subject consented to trial participation does not constitute an AE and should therefore not be reported as AE or SAE. Hospitalization for elective treatment of a pre-existing condition which did not worsen from the subject consented to trial participation is not considered an AE and should therefore not be reported as AE or SAE, even if not planned before consent to trial participation. Hospitalization for routine scheduled treatment or monitoring not associated with any aggravation of the condition does not constitute an AE and should therefore not be reported as AE or SAE. Hospitalization for administrative purpose does not constitute an AE and should therefore not be reported as AE or SAE. Complications that occur during hospitalization are AEs. If a complication prolongs hospitalization, the event is an SAE. When in doubt as to whether hospitalization occurred, the AE should be considered serious.

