### Cohort 2:

Procedural complications will be presented and tabulated according to MedDRA classification. Descriptions of procedural complications will include the start date, the stop date (if it resolved), the severity and seriousness of the procedural complication, and the outcome.

Reported procedural complications will be summarized by the number of subjects reporting the events, as well as by SOC, PT, severity, and seriousness. For the summary of procedural complications by severity, each subject will be counted only once within a SOC or a PT by using the procedural complications with the highest intensity within each category for each analysis.

All information pertaining to procedural complications noted during the trial will be listed by subject, detailing verbatim, SOC, PT, start date, stop date, intensity, and outcome. The procedural complication onset will also be shown relative (in number of days) to the Day 1 skin sample collection.

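### The Cohort 2 definition of a serious procedural complication omits the medically important criterion, so events serious on that ground alone escape 24-hour reporting

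*Combined protocol and SAP*

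**What the plan says.** The protocol runs two event-reporting systems. Section 8.5 is limited by its heading to Cohort 1. Section 8.6 covers the healthy volunteers: "For subjects in Cohort 2, procedural complications will be reported instead of AEs".

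For Cohort 1, Section 8.5.3 gives six criteria for seriousness. The last reads in part: "Is a medically important condition. Events that may not be immediately life-threatening or result in death or hospitalization but may jeopardize the subject". It is illustrated: "Examples are intensive treatment in an emergency room or at home for allergic bronchospasm, blood dyscrasias, and convulsions that do not result in hospitalization".

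For Cohort 2, Section 8.6 states that "a serious procedural complication is any untoward medical event related to the trial procedures that has any of the following consequences". Four criteria follow, and the list ends with "Results in persistent or significant disability/incapacity". A complication that meets one of them goes on a serious procedural complication form, following the instructions in Section 8.5.7, where the limit is 24 hours from knowledge of the event. All other complications are recorded in the source document and eCRF.

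The Cohort 2 part of Section 9.3.4.1 uses the classification directly. Complications are to be described by, among other items, "the severity and seriousness of the procedural complication, and the outcome", and summarized by seriousness.

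**The concern.** The biopsy hazard is common to the two cohorts. The opening text of Section 8.3.1 on cleaning, disinfecting and anaesthetizing the skin applies to both, and each subject has two 4-mm biopsies on Day 1. One would expect a reaction to that procedure to be graded serious by the same standard whoever has it. Under the current wording it is not, for one class of event.

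The people affected are healthy volunteers, for whom Section 2.2.2 anticipates no benefit beyond medical evaluation and whose follow-up visit is optional. What is at stake is whether a significant but non-admitted reaction in a volunteer reaches the sponsor's safety unit within 24 hours, and whether it appears as serious in the Cohort 2 table.

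**Working it through.** No figure in the plan is involved, so the check is a comparison of definitions followed by a trace of the reporting rule.

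**Step 1: the two lists side by side.**

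| Criterion | Section 8.5.3 (Cohort 1) | Section 8.6 (Cohort 2) |
|---|---|---|
| Death | yes | yes |
| Life-threatening | yes | yes |
| Admission or longer hospital stay | yes | yes |
| Lasting or significant disability | yes | yes |
| Congenital anomaly | yes | no |
| Medically important | yes | no |
| Count | 6 | 4 |

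The difference is 6 − 4 = 2 criteria. The first, "Is a congenital anomaly/birth defect", has little practical meaning in a postmenopausal cohort. The second does have meaning there.

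**Step 2: does anything bring the missing criterion back?** Section 8.6 refers to Section 8.5.7, but only for complications that meet the criteria just listed in Section 8.6. Section 8.5.7 defines its own scope through AEs, a category that Cohort 2 does not have. The note on threat to life in Section 8.6 confines that criterion to actual risk of death at the time. No other section supplies the item.

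**Step 3: would Cohort 1 capture the same event?** Yes. Section 8.5.5 records AEs and SAEs from signature of consent, so the Day 1 biopsies are covered although they precede the first application. The SAE report in Section 8.5.7 asks about relationship to the trial procedure as well as to the product.

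**Step 4: one event, two classifications.** Take a first reaction to local anaesthetic with bronchospasm that the investigator attributes to the procedure. It is treated intensively in an emergency room. The subject is not admitted, is judged not to have been at risk of death, and has no lasting disability.

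- Cohort 1: none of the first five criteria is met, the sixth is. The event is an SAE, reported within 24 hours.
- Cohort 2: none of the four criteria is met. The event is a non-serious procedural complication, entered in the source document and eCRF, with no 24-hour report.

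**Step 5: where the classifications agree.** If the same reaction is fatal, life-threatening, disabling or leads to admission, it is serious under both sections. The gap consists only of events whose sole qualifying criterion is medical importance.

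**The case against.** The best defence is that the shorter list is deliberate. Cohort 2 receives no investigational product, has its own reporting system, and the definition is expressly made for the purpose of this trial. Dropping congenital anomaly fits that reading. This accounts for reporting complications instead of AEs, and for the congenital anomaly item. It does not account for a narrower meaning of serious for the same biopsy, and no reason is given.

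A second defence is that the residual risk is small. Exclusion criterion 5 removes anyone in either cohort with a known history of reaction to local anaesthetics, and an investigator could judge a severe bronchospasm life-threatening. Both points stand and narrow the gap. A first reaction is not screened out, however, and Section 8.5.3 itself treats medical importance as covering events that are not immediately life-threatening.

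A reader might also infer more than the documents support:

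- *Any biopsy or anaesthetic reaction is classified differently in the two cohorts.* It is not; see Step 5.
- *The sponsor would not learn of the event.* Every complication goes into the web-based eCRF and is listed by subject with verbatim term, intensity, dates and outcome. There is one site, so the team doing the Cohort 1 biopsies would know as well. What is lost is the 24-hour clock.
- *Procedural complications are the only safety information in Cohort 2.* Section 4.1 also provides for review of changes in health after sampling; it is the planned tabulation that is limited to complications.
- *A comparison of the cohorts would be biased.* Safety is summarized descriptively per cohort, and no comparison of seriousness between cohorts is planned.

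The serious procedural complication form and the guidance printed on the SAE form are not part of the documents, so what they say is unknown.

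**Conclusion.** The inconsistency is real and narrow. Sections 8.5.3 and 8.6 apply different standards of seriousness to the same procedure, and nothing in the protocol closes or justifies the difference for medically important events.

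The impact is small. About 5 subjects are planned for Cohort 2, with one biopsy session each, so few or no affected events are expected. The documents give no event rate from which to put a number on this. The consequences are limited to the missing 24-hour report and the serious/non-serious split in the Cohort 2 table. No endpoint, efficacy analysis or inferential result changes.

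The conclusion assumes that Section 8.6 is applied as written, and that the forms that cannot be seen do not add the criterion. It is worth correcting because it concerns the protection of volunteers and the correction is very cheap.

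**What to change.** Add one bullet to the list of consequences in Section 8.6: *Is a medically important condition, as defined in Section 8.5.3.* Reporting under Section 8.5.7 and the seriousness summary in Section 9.3.4.1 then follow without further edits. The serious procedural complication form should be checked so that it offers the same criterion.

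The cost is one line in an amendment and possibly an additional report form during the trial. No visit, procedure or analysis is added. If the shorter list is intended, a sentence in Section 8.6 giving the reason is the minimum.

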## 9 STATISTICAL CONSIDERATIONS

### 9.1 Sample Size Determination

From Del Duca et al. (2020) paper, the difference in log2-fold changes (SD\*) between FFA patients and healthy controls are reported to 4.851 (4.411), 5.298 (5.512) and 4.559 (4.891) for CXCL9, CXCL10 and IFN- $\gamma$ , respectively.

A sample 30 subjects are randomized in an equal manner (1:1) to delgocitinib cream 20 mg/g or vehicle cream. It is expected that a reduction of at least 90% from baseline to Week 12 for the delgocitinib cream 20 mg/g treated subjects compared to only 5% in the vehicle group, normalized to healthy controls, will be observed.

With the above assumptions, the trial should have at least 80% disjunctive power, i.e. a statistically significant difference (tested at 5% one-sided level in an independent two-sample t-test) can be shown with at least 80% probability, in at least one of the genes, assuming no correlation between the tests and same level of variation as reported in the Del Duca et al. (2020) paper.

\*Derived from the reported p-values coming from a t-test comparing lesional FFA biopsy data (N=12) to data from healthy controls (N=8).

### 9.2 Populations for Analyses

#### Cohort 1:

Efficacy will be evaluated on the basis of the full analysis set (FAS). A supportive analysis will also be conducted on the per-protocol (PP) analysis set.

*Full analysis set (FAS):* All subjects randomised and exposed to IMP will be included in the FAS and will be analysed based on the randomised treatment allocation. Exclusions from the FAS can be considered in special cases as described in ICH E9, Section 5.2.1, Full Analysis Set. If it is decided to exclude a subject from the FAS, a justification addressing ICH E9 will be given.

*PD analysis set:* This analysis set is a subset of the FAS and will include all subjects who have at least one assessment of PD parameters.

*Per-protocol (PP) analysis set:* This analysis set will include all subjects who were randomized, who received at least one dose of IMP and who at least one post dose efficacy measurement with no major protocol deviations affecting the efficacy evaluations. All subjects will be analyzed according to the treatment group that they actually received during the vehicle-controlled period.

*Safety analysis set (vehicle-controlled treatment period):* This analysis set will include all subjects who received at least one dose of the IMP. All subjects will be analyzed according to the treatment group that they actually received during the vehicle-controlled period.

*Safety analysis set (OLE):* This analysis set will include all subjects who entered the OLE and received at least one dose of delgocitinib 20 mg/g during the OLE.

Cohort 2:

*Safety analysis set:* This analysis set will include all subjects who had at least one skin sample collected.

## 9.3 Statistical Analyses

### 9.3.1 General Approach

Continuous variables will be summarized in tables and will include the number of subjects, mean, standard deviation (SD), median, minimum, maximum, first (Q1) and third (Q3) quartiles. Categorical variables will be presented in tables as frequencies and percentages.

All details regarding the efficacy and safety variable definitions, analyses strategy, statistical justification, and techniques for handling missing values will be detailed in a separate statistical analysis plan (SAP) that will be prepared before the database is locked and any analyses are undertaken. Any deviation(s) from the SAP will be described and justified in the final report, as appropriate. Statistical analysis related to molecular signature changes/PD analyses (ie, skin biopsies, tape strips, and skin microbiome) will be described in a separate SAP prepared by the specialty laboratory in charge of these analyses.

All statistical tests will be two-sided and will be performed with a significant level of 0.05, unless otherwise specified in the SAP.

### 9.3.2 Baseline

Baseline will be defined separately for the vehicle-controlled treatment period and OLE as follows:

- Vehicle-controlled treatment period:

For both the safety and exploratory efficacy analyses, the baseline will be defined as the last non-missing assessment prior to the first trial treatment dose (including unscheduled assessments). If the last non-missing assessment is performed on the same date as the first trial treatment and time is not available, the assessment will be considered as baseline, except for AEs and medications starting on the first trial treatment dose date which will be considered post-baseline.

- Open-label extension period:

For the safety analyses, the OLE baseline will be defined as the last non-missing assessment prior to the first delgocitinib cream 20 mg/g dose. This definition will be used for summarizing the change from the OLE baseline for the subject who entered OLE period.

For the exploratory efficacy analyses, the baseline will be defined as the last non-missing assessment prior to the first trial treatment dose (including unscheduled assessments) from the vehicle-controlled treatment period for all subjects.

Change from baseline is defined for both the vehicle-controlled treatment period and OLE as the post-baseline value minus the baseline value unless otherwise specified. Percent change from baseline will be calculated as follows: Percent change from baseline = (Change from baseline / Baseline) x 100

For the pruritus NRS, burning sensation NRS, and pain NRS, the baseline scores will be defined as the average of all non-missing daily 24-hour NRS scores reported over the last 7 days prior to randomization (prior to the first application of the IMP).

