#### **8.1.4 Pruritus Numerical Rating Scale**

The intensity of pruritus due to FFA will be recorded using a NRS. It will be assessed daily starting approximately 7 days prior to Day 1 and up to Day 8. Thereafter, it will be assessed only at the visits specified in [Table 1](#). This will be evaluated by asking subjects to assign a numerical score representing of the worst intensity over the last 24 hours of their symptoms on a scale from 0 to 10, with 0 indicating no symptoms and 10 indicating the worst imaginable symptoms. The NRS of pruritus is presented in [Appendix C](#).

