#### 9.3.3.2 Open-Label Extension Period

These efficacy outcomes will be measured at scheduled visits after Week 12. The following endpoints will be assessed in the OLE:

- Continuous variables: observed value and change (percent) from baseline in LPPAI, FFASS, target area perifollicular scale score, target area perifollicular erythema score, pruritus NRS, burning sensation NRS, pain NRS, and target area hair counts/trichoscopy via fotofinder trichovision.

The above endpoints will be summarized by visit using descriptive statistics with following considerations:

- Summaries will be provided for 1) treatment group in OLE and for 2) randomized treatment groups in the vehicle-controlled treatment period.
- Change from baseline in continuous variables will be analyzed using change from vehicle-controlled treatment period baseline.

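### Percent change is planned for the three NRS scores in the open-label extension, although their baseline can be 0 or a fraction of a point

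*Combined protocol and SAP*

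**What the plan says.** Section 9.3.2 gives one general formula: "Percent change from baseline = (Change from baseline / Baseline) x 100". It makes no exception for a zero or very small baseline.

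Section 9.3.3.2 lists the continuous OLE outcomes as "observed value and change (percent) from baseline in LPPAI, FFASS, target area perifollicular scale score, target area perifollicular erythema score, pruritus NRS", and the list goes on to burning sensation NRS, pain NRS and hair counts. It adds that "The above endpoints will be summarized by visit using descriptive statistics", with change measured from the baseline of the vehicle-controlled period. The standard set of statistics in Section 9.3.1 covers "number of subjects, mean, standard deviation (SD), median, minimum, maximum" and the quartiles.

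For the three NRS scores, Section 9.3.2 takes as baseline the "average of all non-missing daily 24-hour NRS scores reported over the last 7 days" before randomization. Section 8.1.4 has subjects rate pruritus "on a scale from 0 to 10, with 0 indicating no symptoms"; Sections 8.1.5 and 8.1.6 use the same scale for burning sensation and pain.

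The severity requirement at entry (inclusion criterion 6) concerns perifollicular erythema and scale, each at least 2. No criterion requires any itch, burning or pain. Baseline NRS floors of 3 and 4 appear in Section 3, but only for the 3-point and 4-point responder proportions.

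**The concern.** A percent change needs a baseline that is safely above zero, and nothing in the plan secures this for the NRS scores. Section 2.1.1 describes pruritus and trichodynia as features that may occur, so subjects with little or no symptom are plausible.

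Two things then go wrong in the percent-change tables. Subjects with a baseline of 0 have no value and drop out. Because 0 is the bottom of the scale, none of them could have improved, so the loss is one-directional. Subjects with a small fractional baseline can produce values in the hundreds or thousands of percent, which swamp the mean and SD of a group of about 15. A reader of such a table could see average worsening in a group where nearly everyone improved.

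**Working it through.** The plan states no figure on this point, so there is none to reproduce. The check applies the plan's own formula to baselines that its own definitions allow.

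**Inputs from the documents.** NRS 0 to 10 (Sections 8.1.4 to 8.1.6); NRS baseline a 7-day mean of daily whole-number scores (9.3.2); about 30 subjects randomized 1:1, so about 15 per arm (6.3); mean, SD, median, minimum, maximum and quartiles reported (9.3.1). With seven scores the smallest non-zero baseline is 1/7 = 0.14.

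**One subject.** Percent change = 100 x (post - baseline) / baseline.

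| Baseline | Post 0 | Post 1 | Post 2 | Post 3 | Post 10 |
|---|---|---|---|---|---|
| 0 | undefined | undefined | undefined | undefined | undefined |
| 1/7 | -100% | +600% | +1300% | +2000% | +6900% |
| 0.5 | -100% | +100% | +300% | +500% | +1900% |
| 3 | -100% | -66.7% | -33.3% | 0% | +233% |

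For example, 100 x (2 - 1/7) / (1/7) = +1300%.

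**One group (assumed data).** All subjects but one halve their score (-50%); the remaining one starts at 1/7 and ends at 2.

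- n = 15: (14 x (-50) + 1300) / 15 = +40.0%; SD 349; median -50%.
- n = 30: (29 x (-50) + 1300) / 30 = -5.0%; median -50%.
- If that subject ends at 1, 3 or 5 instead, the mean is -6.7%, +86.7% or +180.0% for n = 15, and -28.3%, +18.3% or +65.0% for n = 30.
- Mean absolute change for n = 15, if the 14 go from 4 to 2: (14 x (-2) + 1.86) / 15 = -1.74 points.

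**Simulation (assumed distributions).** Daily scores are Poisson, baseline is the mean of seven, and the later value is a single score. In the reference case, 40% of subjects have a mean daily score of 0.2 and do not change; the rest have a mean of 4 and improve by 40%. In arms of 15:

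- Mean percent change was positive, that is, in the wrong direction, in 20.8% of arms; mean absolute change in 0.7%.
- Undefined values averaged 15 x 0.4 x exp(-7 x 0.2) = 1.5 subjects per arm.

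Two sets of variations give the range for arms of 15:

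- 40% nearly symptom-free, their mean daily score 0.1 to 0.5, the others 3 to 5, with or without improvement in the low group: 6.5% to 32% for mean percent change, 0.1% to 2.1% for mean absolute change, at most 2.3% for median percent change. Limiting percent change to baseline of at least 3 brought the mean down to 0.4% to 1.7%.
- 10% to 40% nearly symptom-free, their mean daily score 0.1 to 0.3, the others 3 or 5: about 4% to 29% for mean percent change, at most 0.9% for its median. For pooled groups of 30 the mean gave about 1% to 24%.

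**Other variables on the list.** The target-area scores are at least 2 at entry. FFASS is at least 2 x 1 + 1 + 1 = 4 by the Appendix B grades. LPPAI is at least (2 + 2)/3 = 1.33 if its scalp signs match the target-area scores. These do not share the problem. Hair counts have no stated floor.

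**The case against.** The strongest reply is that little rests on these columns, and most of it stands. Observed NRS values are planned at every OLE visit, including for subjects with baseline 0. On the natural reading absolute change is tabulated too, since Section 9.3.2 defines it for the OLE. Median and quartiles are already planned, and the median is barely moved by the outliers. Comparing the number of subjects in the percent-change and observed-value cells would show how many were lost. One of the two planned summaries is by OLE treatment, pooling about 30 subjects, where a single outlier ending at 2 does not flip the sign. Percent change is not among the Section 3 endpoints, and the OLE summaries carry no test or decision rule.

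Nor is every large percentage trivial: +2000% from 1/7 is a rise of 2.86 points, close to the 3-point responder threshold.

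A reader might infer that the OLE has no other NRS evidence, or that symptom-free subjects vanish from it. The documents do not support that, because the observed values remain. A reader might also infer that the comparison with vehicle is distorted. It is not: the synopsis specifies absolute change as the dependent variable of the MMRM.

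Section 9.3.1 also defers variable definitions to a separate SAP, which may hold a zero-baseline convention that cannot be seen here. That is a good place for the correction. But the formula and the list of variables are already set in the protocol, and the median cannot restore values that do not exist.

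**Conclusion.** The point holds, with a narrow scope. As written, Sections 9.3.2 and 9.3.3.2 prescribe a statistic that is undefined for some permitted NRS baselines and unstable for others. The arithmetic for the single subject and the worked groups follows directly from the plan's formula. The 4% to 32% range rests on assumed score distributions and an assumed 40% improvement; it shows that the problem need not be rare, not how often it will occur in this trial. The number of subjects with baseline 0 is likewise unknown.

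The damage is confined to the percent-change columns for three scores in descriptive, exploratory OLE tables, and there mainly to the mean, SD and maximum and to the missing zero-baseline subjects. The primary molecular endpoint and the vehicle-controlled MMRM are untouched. It is worth correcting because the correction is simple and a mean of the wrong sign is easily quoted out of context.

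**What to change.** In Sections 9.3.2 and 9.3.3.2, or in the SAP before database lock, state that the three NRS scores are summarised in the OLE by observed value and absolute change in all subjects, and drop percent change for them. Absolute change is defined for everyone with both values and lies between -10 and +10.

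If percent change is kept, limit it to subjects with a baseline NRS of at least 3, the floor already used for the 3-point responder endpoint. Values then lie between -100% and +233%. Rely on the median and quartiles, and state the number of subjects excluded.

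The cost is a sentence or two of text; design, sample size and data collection do not change. The downside of the second option is coverage. If 40% of subjects are nearly symptom-free, it leaves out at least about 6 of 15 per arm (0.4 x 15), against about 1.5 who are undefined in the reference case now. The all-subject table of absolute change should therefore stand beside it.
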